8.3.4 Analysis of Other Endpoints

8.3.4.1 Definition of Variables

Body Mass Index (BMI): The BMI at each visit is calculated using the weight and height at each visit as follows:

$$\text{BMI} = \frac{\text{Weight (kg)}}{\text{Height}^2 \text{ (m}^2\text{)}}$$

BMI z-score: The BMI-for-age z-score, adjusted for age and sex, will be referred to as BMI z-score. The BMI z-score will be calculated using the Centers for Disease Control and Prevention (CDC) growth charts⁹, with age (in months) used for the calculation defined in [Appendix](#).

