**Table 3-2 Study VX20-121-102: Run-in Period, Treatment Period, and Safety Follow-up Visit**

Event/Assessment a	Run-in Period		Treatment Period b						ETT Visit c	Safety Follow-up Visit 28 (± 7) Days After the Last Dose of Study Drug (If Applicable) d	Comments
	Day -28 (± 1 Day)	Day -14 (Day -15 to Day -3)	Day 1	Day 15 (± 3 Days)	Weeks 4, 8, 12, 16 (± 5 Days)	Weeks 20, 28, 32, 40, 44, 48 (± 5 Days)	Weeks 24 and 36 (± 5 Days)	Week 52 (± 5 Days)			
TSQM	X		X					X	X		May be completed within 5 days prior to the study visit. All questionnaires completed on the day of the study visit must be completed prior to any other assessments, with CFQ-R completed first. All subjects will complete the TSQM at the Day -28 Visit; only subjects <18 years of age on the date of informed consent will complete the TSQM at subsequent visits (Section 11.4.5).
CF-IQ	X		X		Week 4		Week 24	X			May be completed within 5 days prior to the study visit. CF-IQ, PGIS, and PGIC must be completed on the same day, and CF-IQ must be performed before PGIS and PGIC (as applicable). All questionnaires completed on the day of the study visit must be completed prior to any other assessments, with CFQ-R completed first (Section 11.4.6).
PGIS	X		X		Week 4						
PGIC			X		Week 4						
Height and weight	X		X	X	Weeks 4, 8, 16		X	X	X	X	Measured with shoes off. Following screening, height will be collected only for subjects ≤21 years of age on the date of informed consent

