### 9.1.1 Screening

Screening Visit assessments are listed in [Table 3-1](#).

The Screening Period (Day -56 through Day -29) will occur within 28 days before the first dose of ELX/TEZ/IVA in the Run-in Period.

Screening assessments will be used to confirm that subjects meet the eligibility criteria. The investigator (or an appropriate authorized designee) will obtain informed consent and assent, if applicable, from each subject before any study procedure takes place.

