### 11.1 Subject and Disease Characteristics

Subject and disease characteristics include the following: demographics, medical history, height, and weight.

Medical history will be elicited from each subject and extracted from medical records during screening. Based on the medical history, the subject will be assessed for any disqualifying medical conditions as specified in the inclusion and exclusion criteria. The medical history will include a complete review of systems, medical and surgical histories, and any allergies.

Height and weight will be measured with shoes off. Height will be collected at screening for all subjects. Following screening, height will be collected only for subjects  $\leq 21$  years of age on the date of informed consent.

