#### **11.5.5 Height and Weight**

Height and weight will be measured with shoes off. Height will be collected at screening for all subjects. Following screening, height will be collected only for subjects  $\leq 21$  years of age on the date of informed consent.

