8 STATISTICAL ANALYSIS

8.1 General Considerations

The Schedule of Assessments is provided in the CSP for Study 102. The precision standards for reporting safety and efficacy variables are provided in an internal Biometrics document that specifies the programming rules including the precision for derived variables.

Continuous variables will be summarized using the following descriptive summary statistics: the number of subjects (n), mean, SD, median, minimum value (min), and maximum value (max).

Categorical variables will be summarized using counts and percentages. Percentages will be presented to 1 decimal place.

Baseline value:

For all safety endpoints:

- Unless otherwise specified, baseline will be defined as the most recent non-missing measurement (scheduled or unscheduled) collected before the first dose of study drug in the Treatment Period (i.e., the Day 1 Visit).

For all efficacy endpoints:

- Except for SwCl, baseline will be defined as the pre-dose Day 1 value. If the pre-dose Day 1 value is missing, the most recent pre-dose, non-missing value on or after the Day -14 visit, including unscheduled visits, will be used as baseline.
- For SwCl, baseline will be defined as the average of the two most recent pre-dose, non-missing values on or after the Day -14 visit, including unscheduled visits. If only 1 non-missing value is available during this interval, the available value will be considered as baseline.

Absolute change from baseline will be calculated as post-baseline value - baseline value.

Relative change from baseline will be calculated as (post-baseline value - baseline value)/baseline value.

The **Treatment-emergent (TE) Period for the Run-in Period** will be from the first dose date of study drug in the Run-in Period to (1) the first dose date of study drug in the Treatment Period for subjects who complete the Run-in Period and continue to the Treatment Period, or (2) 28 days after the last dose date of study drug in the Run-in Period or to the completion of study participation date, whichever occurs first, for subjects who do not continue to the Treatment Period (e.g., subjects who do not meet the conditions to enter the Treatment Period).

The **TE Period for the Treatment Period** will be from the first dose date of study drug in the Treatment Period (VNZ/TEZ/D-IVA or ELX/TEZ/IVA) to 28 days after the last dose date of study drug in the Treatment Period or to the completion of study participation date, whichever occurs first.

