Appendix C: Details of GLI Equations for Calculating ppFEV₁

Percent predicted values will be calculated for the parameters of FEV₁, FVC, FEV₁/FVC, and FEF_{25%-75%} using the Quanjer GLI-2012 Regression Equations and Lookup Tables.

The regression equations and lookup tables required to implement the Quanjer GLI-2012 predicted values are available in:

Philip H. Quanjer, Sanja Stanojevic, Tim J. Cole, Janet Stocks. Quanjer GLI-2012 Regression Equation and Lookup Tables. Global Lung Function Initiative. [online] Available at: <https://www.ers-education.org/lr/show-details/?idP=138978> [Accessed Sep 2023].

The instructions and tools on how to implement the Quanjer GLI-2012 equations are:

Philip H. Quanjer, Sanja Stanojevic, Tim J. Cole, Janet Stocks. Implementing GLI-2012 regression equations. Global Lung Function Initiative. [online] Available at: <https://www.ers-education.org/lr/show-details/?idP=138979> [Accessed Sep 2023].

Sanja Stanojevic. GLI-2012 - SAS Macro. Global Lung Function Initiative. [online] Available at: <https://www.ers-education.org/lr/show-details/?idP=138988> [Accessed Sep 2023].

The data handling rule for spirometry is as follows:

- Input age with at least 2 decimal places
- Use height at screening, regardless of if height is collected at other study visits, for subjects whose age at informed consent is >21 years. For subjects with age ≤21 years, height collected at the respective visit should be used.
- For race, race is Black if, on the CRF, Black or African American is the only race selected. Race is Northeast Asian if Northeast Asian is the only race selected. Race is Southeast Asian if Southeast Asian is the only race selected. Race is White if White is the only race selected. Race is Other for all other races, including multiple selections.

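### BMI is defined from same-visit height, which is not collected after screening in subjects over 21, so read literally they drop out of the Week 52 BMI analysis

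*SAP*

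**What the plan says.** - **BMI definition (SAP 8.3.4.1).** "The BMI at each visit is calculated using the weight and height at each visit as follows", followed by weight in kg divided by squared height in metres. No other source of height is named.
- **Height collection (Protocol 11.1, 11.5.5 and Table 3-2).** "Height will be collected at screening for all subjects". After that, "Following screening, height will be collected only for subjects ≤21 years of age on the date of informed consent". Weight continues to be measured in everyone.
- **Analysis windows (SAP Appendix A).** Height, weight, BMI and z-scores form one row under the efficacy assessments. Note 2a makes a measurement missing for a visit when no numerical value falls in that visit's window.
- **Efficacy baseline (SAP 8.1).** "Except for SwCl, baseline will be defined as the pre-dose Day 1 value". If that is missing, the fallback is "the most recent pre-dose, non-missing value on or after the Day -14 visit".
- **Other baseline wording.** Protocol 12.3.1 takes the last non-missing value before the first Treatment Period dose. The Appendix A baseline window is anything pre-dose up to Day 1. Neither has a Day -14 lower limit.
- **Screening height (SAP Appendix C).** For subjects over 21 at consent: "Use height at screening, regardless of if height is collected at other study visits". For those aged 21 or younger, the height at the respective visit is used. The rule is introduced as data handling for spirometry.
- **BMI analysis (SAP 8.3.4.2).** An MMRM of change in BMI on data from Day 15 to Week 52, with no age limit stated. BMI z-score, by contrast, is limited to subjects aged 20 or younger at baseline.

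**The concern.** The BMI definition calls for a height that the protocol deliberately does not collect in subjects over 21. This goes beyond silence about a detail: the SAP names the input (height at the visit) and also says what happens when a measurement is unavailable (missing for the visit). The two rules together remove a whole age group from an endpoint that carries no age limit. The Week 52 treatment difference in BMI would then describe adolescents and young adults only, in a table that appears to cover the full analysis set. The sensible alternative is to use screening height. It is already written into the SAP for spirometry but not for BMI, so a programmer applying it to BMI would be departing from the text.

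**Working it through.** The plan states no power or sample-size figure for BMI, so there is none to reproduce. The check is a side-by-side reading for a subject over 21 at consent.

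1. **Post-baseline BMI.** The formula needs weight and height at the visit. Weight is scheduled at Day 15 and Weeks 4, 8, 16, 24, 36 and 52. Height is scheduled at none of these for this subject.
2. **Could screening height fall into a post-baseline window?** No. Screening runs from Day -56 to Day -29, and the post-baseline windows for this row start at Day 1. Note 2a therefore makes height missing at every scheduled post-baseline visit, and BMI cannot be formed. An unscheduled height could supply an isolated value.
3. **Baseline BMI.** Under SAP 8.1 a value must be from Day 1 or from the Day -14 visit onwards. That visit may take place from Day -15. The last screening day is Day -29, which is (-15) - (-29) = 14 days too early, so a screening height or BMI does not qualify. Under Protocol 12.3.1 or the Appendix A window it could. The documents point both ways.
4. **Change from baseline.** Change is the post-baseline value minus the baseline value. By step 2 the first term is missing whichever baseline rule applies, so the subject contributes nothing to the BMI MMRM.
5. **Does another rule rescue it?** Appendix C would, but it is limited to spirometry. Nothing else in the protocol or SAP assigns a height to this subject after screening.
6. **BMI z-score.** This is unaffected: a subject aged 20 or younger at baseline was also 20 or younger at consent, so height is scheduled.

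**Scale.** The age distribution is not in the documents; entry is from 12 years with no upper limit. The shares below are assumptions. With about 400 planned, n = 400 × share. The standard error relative to the full set is √(400/n), taking the same SD in both sets.

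| Assumed share aged 21 or younger | Remaining | Lost | Standard error ratio |
|---|---|---|---|
| 15% | 60 | 340 | √(400/60) = 2.6 |
| 25% | 100 | 300 | √(400/100) = 2.0 |
| 40% | 160 | 240 | √(400/160) = 1.6 |
| 50% | 200 | 200 | √(400/200) = 1.4 |

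With the Appendix C height rule applied to BMI, BMI can be computed at every visit with a weight, and the whole full analysis set can enter.

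**The case against.** The strongest reply is that the intent is plain. Height is measured in everyone at screening, the protocol stops measuring it at an age when repeating it was judged unnecessary, and the same SAP uses screening height for exactly this group in Appendix C. SAP 8.3.4.2 limits z-score by age but not BMI, and SAP 8.2.2 plans height and BMI summaries for the whole full analysis set. A competent programmer would probably use screening height. SAP 8.1 also mentions an internal programming document covering derived variables, which may say so.

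The point about intent stands, and it is why the loss should be called unintended. It does not make the text deliver that intent. The internal document is not available to the reader, and it cannot be assumed to override the SAP's own definition and missing-data note.

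The reply on consequences also stands. BMI is listed among the other endpoints and is outside the hierarchy in SAP 8.3.2.3. With height held fixed at H, change in BMI is (weight at Week 52 - baseline weight)/H², so the separately analysed weight endpoint already carries most of the information in these subjects.

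Three stronger readings are tempting but not supported:
- A reader might infer that the SAP restricts the BMI endpoint to subjects aged 21 or younger. No such rule is written; the restriction is a by-product of other rules.
- A reader might infer that baseline BMI, and the baseline height and BMI summaries, do not exist for subjects over 21. That follows only if the Day -14 limit in SAP 8.1 governs. It is written for efficacy endpoints, whereas SAP 8.2.2 treats height as a background characteristic, and Appendix A and Protocol 12.3.1 are looser.
- A reader might infer that most adults are lost. No age distribution is given, so this cannot be established.

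**Conclusion.** The point holds as a minor defect in a definition. Applied as written, SAP 8.3.4.1 with Appendix A note 2a leaves every subject over 21 at consent without any scheduled post-baseline BMI, and so outside the Week 52 BMI change analysis. This rests on reading the SAP literally and on no unscheduled heights being taken. It does not depend on which baseline rule governs; that matters only for baseline BMI and the baseline summaries. The number of subjects affected cannot be stated from the documents, so the range shown is illustrative. The primary and key secondary endpoints, the weight endpoint and BMI z-score are untouched.

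**What to change.** Add to SAP 8.3.4.1 that, for subjects over 21 at informed consent, BMI at all visits including baseline uses screening height, and that for subjects aged 21 or younger it uses the height at the respective visit. This is the Appendix C rule with its scope widened. State in the same place that it also applies to the baseline height and BMI summaries in SAP 8.2.2, which settles the baseline question for these two variables.

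The cost is a sentence or two in the SAP, made by amendment before database lock as SAP Section 3 provides. No new data and no protocol change are needed.

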8.3.4.2 Analysis Method

Proportion of subjects with SwCl <60 mmol/L through Week 52 (within-study): Analysis of this endpoint will be based on a GEE model similar to that for the proportion of subjects with SwCl <60 through Week 24 using the FAS (8.3.3.2), with the addition of data from Week 36 and Week 52.

Proportion of subjects with SwCl <30 mmol/L through Week 52 (within-study): Analysis of this endpoint will be based on a GEE model similar to that for the proportion of subjects with SwCl <30 through Week 24 using the FAS (8.3.3.2), with the addition of data from Week 36 and Week 52.

Absolute change from baseline in BMI at Week 52: Analysis of this variable will be based on an MMRM similar to the primary analysis of the primary estimand (8.3.1.3). Data obtained from Day 15, Week 4, Week 8, Week 16, Week 24, Week 36, and Week 52 will be included in the

model. The estimated treatment difference at Week 52 will be presented along with the 2-sided 95% CI. The post-baseline raw values and the absolute change from baseline at each post-baseline visit through Week 52 will be summarized descriptively (n, mean, SD, median, min, max), in addition.

Absolute change from baseline in BMI z-score at Week 52 (for subjects ≤ 20 years of age at Baseline): Analysis of this variable will be based on an MMRM similar to the primary analysis of the primary estimand (8.3.1.3), excluding the term age at screening (< 18 versus ≥ 18 years of age), for subjects ≤ 20 years of age at Baseline. Data obtained from Day 15, Week 4, Week 8, Week 16, Week 24, Week 36, and Week 52 will be included in the model. The estimated treatment difference at Week 52 will be presented along with the 2-sided 95% CI. The post-baseline raw values and the absolute change from baseline at each post-baseline visit through Week 52 will be summarized descriptively (n, mean, SD, median, min, max), in addition.

Absolute change from baseline in weight at Week 52: Analysis of this variable will be based on an MMRM similar to the primary analysis of the primary estimand (8.3.1.3). Data obtained from Day 15, Week 4, Week 8, Week 16, Week 24, Week 36, and Week 52 will be included in the model. The estimated treatment difference at Week 52 will be presented along with the 2-sided 95% CI. The post-baseline raw values and the absolute change from baseline at each post-baseline visit through Week 52 will be summarized descriptively (n, mean, SD, median, min, max), in addition.

Absolute change from baseline in CFQ-R RD score through Week 52: Analysis of this domain will be based on an MMRM similar to that for absolute change from baseline in CFQ-R RD score through Week 24 (8.3.3.2), with the addition of data from Week 52. The estimated change through Week 52 will be based on averaging estimates from Weeks 16, 24, and 52. The estimated treatment difference through Week 52 will be presented along with the 2-sided 95% CI. The post-baseline raw values and the absolute change from baseline at each post-baseline visit through Week 52 will be summarized descriptively (n, mean, SD, median, min, max), in addition.

8.3.5 Analysis of Additional Efficacy Variables

8.3.5.1 Analysis of Additional Spirometry Variables

Summary statistics for raw values and for change from baseline of the following spirometry measurements will be presented by treatment group at each visit:

- FEV₁:
 - Absolute change from baseline in FEV₁ (L)
 - Relative change from baseline in FEV₁ (%)
 - Absolute change from baseline in percent predicted FEV₁ (percentage points)
 - Relative change from baseline in percent predicted FEV₁ (%)
- FVC:
 - Absolute change from baseline in FVC (L)
 - Relative change from baseline in FVC (%)
 - Absolute change from baseline in percent predicted FVC (percentage points)

- Relative change from baseline in percent predicted FVC (%)
- FEV₁/FVC:
 - Absolute change from baseline in FEV₁/FVC
 - Relative change from baseline in FEV₁/FVC (%)
 - Absolute change from baseline in percent predicted FEV₁/FVC
 - Relative change from baseline in percent predicted FEV₁/FVC (%)

8.3.5.2 Analysis of Other CFQ-R Variables

Descriptive summary statistics for raw values and for change from baseline of the CFQ-R non-respiratory domain scores will be presented by treatment group at each visit.

8.3.5.3 Analysis of Additional Variables for Pulmonary Exacerbations and Hospitalization

The analysis period for all variables in this section will be the PEx analysis period.

Pulmonary Exacerbations:

In addition to the other secondary endpoint described in 8.3.3.2, PEx will be further analyzed as described below:

- Time-to-first event (in days):
 - Time-to-first PEx
 - Time-to-first PEx requiring hospitalization
 - Time-to-first PEx requiring intravenous (IV) antibiotic therapy
 - Time-to-first PEx requiring hospitalization or IV antibiotic therapy
- Number of events:
 - Number of PEx requiring hospitalizations through Week 52
 - Number of PEx requiring IV antibiotic therapy through Week 52
 - Number of PEx requiring hospitalization or IV antibiotic therapy through Week 52
- Duration of events:
 - Number of days with PEx through Week 52
 - Number of days with PEx requiring hospitalization through Week 52
 - Number of days with PEx requiring IV antibiotic therapy through Week 52
 - Number of days with PEx requiring hospitalization or IV antibiotic therapy through Week 52

Hospitalization:

- Number of events:
 - Number of planned hospitalizations for CF (i.e., antibiotic therapy) through Week 52

- Number of all unplanned hospitalizations for reasons other than antibiotic therapy for sinopulmonary signs/symptoms through Week 52
- Duration of events:
 - Number of days of planned hospitalizations for CF (i.e., antibiotic therapy) through Week 52
 - Number of days of all unplanned hospitalizations for reasons other than antibiotic therapy for sinopulmonary signs/symptoms through Week 52

Analysis of PEx/Hospitalization Variables:

For the time-to-event variables, the analysis time will be the number of days from the first dose date of study drug in the Treatment Period to the date of the first defined event during the PEx analysis period. A subject who does not experience the event during the PEx analysis period will be censored at the PEx analysis period end date for that event. The analysis of time-to-event will be based on the Kaplan Meier method; the corresponding plot will be presented.

For the number of events variables, subjects with multiple defined events during the PEx analysis period will be counted multiple times. A descriptive summary of the number of events along with the observed event rate will be provided.

The annualized duration of events for each subject will be the total number of days with the defined event times 48 weeks, divided by the total number of weeks in the study up to the end of the PEx analysis period. The annualized duration will be descriptively summarized.

8.4 Safety Analysis

All safety analyses will be based on data from the TE Period for the Treatment Period for all subjects in the Safety Set for the Treatment Period, unless otherwise specified. Subjects will be analyzed according to the treatment they actually received in the Treatment Period, as applicable. Subjects receiving study drug from more than one treatment group will be allocated to the VNZ/TEZ/D-IVA group.

The overall safety profile of the study drug will be assessed in terms of the following safety and tolerability endpoints:

- Treatment-emergent adverse events (TEAEs)
- Clinical laboratory values
- ECGs
- Vital signs
- Pulse oximetry
- Ophthalmological examinations (for subjects <18 years of age on the date of informed consent)

Only descriptive analysis of safety will be performed, and no statistical testing will be performed.

8.4.1 Adverse Events

For analysis purposes, AEs will be classified as pretreatment AEs, TEAEs during the Run-in Period, TEAEs during the Treatment Period, or post-treatment AEs, defined as follows:

Pretreatment AE: any AE that occurred before the first dose date of study drug in the Run-in Period

TEAE during the Run-in Period: any AE that worsened (either in severity or seriousness) or that was newly developed on or after the first dose date of study drug in the Run-in Period through the end of the TE Period for the Run-in Period

TEAE during the Treatment Period: any AE that worsened (either in severity or seriousness) or that was newly developed on or after the first dose date of study drug in the Treatment Period through the end of the TE Period for the Treatment Period

Post-treatment AE: any AE that worsened (either in severity or seriousness) or that was newly developed after:

- the TE Period for the Run-in Period if the subject did not receive treatment in the Treatment Period
- the TE Period for the Treatment Period if the subject received treatment in the Treatment Period

For AEs with completely missing or partially missing start dates, if there is no clear evidence that the AEs started before or after study treatment, the AEs will be classified as TEAEs corresponding to the Treatment Period. Unless otherwise specified, TEAE refers to TEAE during the Treatment Period.

Details for imputing missing or partial start dates of adverse events are described in [Appendix](#) .

An overview of all TEAEs by treatment group and overall will be summarized in the following categories:

- Number of TEAEs (total number of TEAEs only)
- Subjects with any TEAEs
- Subjects with TEAEs by strongest relationship
- Subjects with TEAEs by maximum severity
- Subjects with TEAEs leading to study drug discontinuation (discontinuation of any study drugs)
- Subjects with TEAEs leading to study drug interruption (interruption of any study drugs)
- Subjects with Grade 3+ TEAEs
- Subjects with related TEAEs
- Subjects with serious TEAEs
- Subjects with related serious TEAEs
- Subjects with TEAE leading to death

The following summary tables of TEAEs will be presented by treatment group:

- All TEAEs
- TEAEs by strongest relationship
- TEAEs by maximum severity
- TEAEs leading to treatment discontinuation
- TEAEs leading to treatment interruption
- Grade 3+ TEAEs
- Related TEAEs
- Serious TEAEs
- Related serious TEAEs
- TEAEs leading to death

Summaries will be presented by MedDRA SOC and PT using frequency counts and percentages (i.e., number and percentage of subjects with an event). When summarizing the number and percentage of subjects with an event, subjects with multiple occurrences of the same AE or a continuing AE will be counted once, and only the maximum severity level will be presented in the severity summaries and the strongest relationship level in the relationship summaries.

Additional summary tables will be presented by treatment for TEAEs showing number and percentage of subjects:

- All TEAEs by PT

All AEs, including pretreatment AEs, TEAEs for all applicable periods, and post-treatment AEs, will be presented in an individual subject data listing based on the All Subjects Set. In addition, separate listings containing individual subject AE data for TEAEs leading to study drug discontinuation, TEAEs leading to study drug interruption, Grade 3+ TEAEs, all SAEs, and deaths will be provided, with a flag indicating the TEAE status for SAEs and deaths.

The following tables for the Run-in Period will be presented overall based on the Safety Set for the Run-in Period:

- An overview of TEAEs during the Run-in Period
- All TEAEs during the Run-in Period by SOC and PT

